### 1.2.5. Revision History for SAP Amendments

Original SAP Version 1.0 was finalized on 29 May 2020 and was based on Protocol Amendment 1.

Revised SAP Version 2.0 is revised as summarized in Section 1.2.4.2 above.

## 2. INVESTIGATION PLAN

### 2.1. Study Design and Randomization

This is a multicenter, Phase 2, multicenter, randomized, double-blind, multi-dose, parallel-arm, placebo-controlled study designed to evaluate the safety and efficacy of REGN5069 in patients with pain due to osteoarthritis of the knee. Up to approximately 240 patients are randomized in a 1:1:1 ratio to receive a low dose of REGN5069 at 100 mg IV Q4W, a high dose of REGN5069 at 1000 mg IV Q4W, or matching placebo Q4W, for a total of 3 doses Q4W during the 12-week treatment period.

Randomization is stratified by Kellgren-Lawrence (K-L) category (2-3 vs 4) of the index knee joint at the screening visit and participation in the Moticon sub-study (yes vs no). The use of the stratification factor based on participation in the Moticon sub-study ensures balance in the treatment assignments within the Moticon sub-study. The index knee joint is defined as the knee joint affected by OA and selected for primary assessment for this study.

An independent Data Monitoring Committee (IDMC) is monitoring unblinded data. Based on these reviews in the context of the totality of evidence, if there are significant concerns at any time regarding a safety issue, the IDMC may make a recommendation to the sponsor to temporarily pause, alter, or terminate the study. Once recommendations from the IDMC have been received, further discussions may be conducted, if appropriate, and the sponsor is to determine if these or other actions should be taken.

### 2.2. Sample Size and Power Considerations

Up to approximately 240 patients (80 per treatment group) are randomized to 3 treatment groups in a 1:1:1 allocation. Assuming a standard deviation (SD) of 2.3, 80 patients per treatment group provides approximately 80% power to detect a treatment difference of 1.1 between the REGN5069 dose and the matching placebo in change from baseline to week 12 in Western Ontario and McMaster Universities Osteoarthritis Index (WOMAC) pain subscale score (using a significance level of 0.05, 2-sided t-test and assuming a dropout rate of 15% [6% due to lack of efficacy or AEs, and 9% due to other reasons]).

[figure not shown]
The WOMAC index is comprised of 24 parameters grouped in subscales (pain, physical function, stiffness) and is reported using a Numerical Rating Scale score of 1-10.

### 2.3. Study Plan

The study was intended to consist of a screening period of up to 30 days, followed by a 12-week randomized, double-blind, placebo-controlled treatment period, a 24-week follow-up period, and an end-of-study phone call approximately 52 weeks after the first dose of study drug (Figure 1). The purpose of the end-of-study phone call was to determine whether a patient underwent, is scheduled for, or is on a waiting list to receive joint replacement surgery, or whether joint replacement was recommended but the patient elected to defer. Thus, each patient was to be enrolled in the study for approximately 56 weeks, including the screening period and the period up to the end-of-study phone call.

As the Interim Analysis showed no treatment effect, and there were no safety signals observed, it was decided to terminate the study at the time last patient completes week 36 visit; thus, a limited number of study patients will have completed week 52 phone call.

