##### 4.1.2.2. Secondary Safety Endpoints

The secondary safety endpoints of the study are:

- The incidence of treatment-emergent adverse events (TEAEs) in patients treated with REGN5069 compared to patients treated with placebo throughout the study duration

- The incidence of imaging abnormalities consistent with accelerated arthropathies as assessed by X-ray and MRI in patients treated with REGN5069 compared to patients treated with placebo throughout the study duration
- Presence of anti-REGN5069 antibody development in patients treated with REGN5069 compared to patients treated with placebo throughout the study duration

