#### 1.2.4.2. SAP Version 2.0

In this section we summarize the modifications to the original SAP V1.0, as presented in this current version of SAP (V2.0).

After reviewing the interim analysis data from the Phase 2 clinical study (R5069-OA-1849), Regeneron has concluded that the week 12 data did not show significance between the placebo and each of the REGN5069 treatment arms in the WOMAC pain subscale score as well as other efficacy parameters evaluated. Additionally, there were no new safety findings or concerns associated with REGN5069. Based on the failure to demonstrate additional benefit in the REGN5069 dose groups compared to placebo, Regeneron made the decision to discontinue REGN5069 in the OA pain indication. The Phase 2 study (R5069-OA-1849) will be prematurely terminated after all patients have completed the Week 36 visit (visit 10) and will not be required to complete the Week 52 phone call, specified in Schedule of Events (Protocol Amendment 1, Section 8.1).

An abbreviated CSR will now be produced for this study, and this SAP amendment describes analysis changes stemming from this decision.

Table 2 presents the details of these changes from SAP Version 1.0.

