	
Rationale: The number of patients <math>\geq 75</math> is too small for the model to converge. Also provided a clarification on how the subgroup analysis will be presented.

Section 5.8.1 Adverse Events	
Inserted:
 

• All TEAEs by SOC, PT, relationship

• All AEs by SOC, PT

• All SAEs, by study period

• All SAEs by severity and study period

• All SAEs by relationship, treatment and follow-up period

• Listing of TEAEs leading to infusion interruption

 
Follow-up AEs will be summarized similarly as TEAEs, as well as AEs occurring during Treatment and Follow-up Periods combined.

	
Rationale: Provided further clarification on the AE analyses to be performed.

Section 5.8.1 Adverse Events	
Deleted:
 

• Non-serious TEAEs by SOC and PT

• All Joint replacements

 
Rationale: As at the IA there were no safety issues detected, there is no further need to summarize non-serious AEs separately. All AEs and Serious AEs summaries suffice. Also, joint replacement was performed for a single patient, so a summary table is no further necessary, all information collected will be presented in the joint replacement listing.

Sections Changed	Changes and Rationale
Section 5.8.2 Clinical Laboratory Measurements	Deleted: Shift tables based on baseline normal/abnormal and other tabular and graphical methods may be used to present the results for laboratory tests of interest.
	Inserted: For all analytes, plots of change from baseline by visit are to be presented by treatment group.
	Rationale: As at the IA there were no safety issues detected, the PCSV analysis is sufficient, shift tables are no further necessary. Also provided clarification on what figures will be presented for laboratory data.
Appendix 11.2 Reference for Criteria for Treatment- Emergent Potentially Clinically Significant Values (PCSV)	Deleted Conjugated Bilirubin ALT/AST and Total Bilirubin ALT/AST and Total Bilirubin and ALP Total Cholesterol Triglycerides Rationale: As at the IA there were no safety issues detected, these PCSVs were not of further interest.
Appendix 11.2 Reference for Criteria for ... PCSV	Deleted HbA1c Rationale: This analyte was only to be collected at baseline, so no PCSV analysis is to be performed.

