### **5.8.8. Imaging Data**

The number (percentage) of patients with images requiring arthropathy adjudication, as well as the number (percentage) of patients with confirmed adjudicated arthropathy (by type of arthropathy), as well as joint replacements and other findings are to be summarized by treatment group. A KM analysis of time to these events will be provided if data allows. Patient listings of cases confirmed by adjudication are to also be provided, as well as of clinically significant imaging findings that did not require adjudication.

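### The imaging analysis in SAP 5.8.8 gives no confidence interval, no contrast with placebo and no combined REGN5069 group for adjudicated arthropathy, a comparative secondary safety endpoint

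*SAP*

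**What the plan says.** Protocol 4.1.2.2 lists a secondary safety endpoint that covers the whole study and has placebo as its comparator; its text runs "The incidence of imaging abnormalities consistent with accelerated arthropathies as assessed by X-ray and MRI in patients treated with REGN5069 compared to patients treated with" and then names the control. Protocol 3.2.1 explains the imaging programme. Agents that block NGF have raised concerns, arthropathy in particular, and regular X-ray and MRI are included as a precaution.

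For the analysis, SAP 5.8.8 provides, for each treatment group, that "the number (percentage) of patients with confirmed adjudicated arthropathy (by type of arthropathy), as well as joint replacements and other findings are to be summarized". It adds the number of patients with images needing adjudication, listings, and a Kaplan-Meier analysis if the data permit. It names no interval, no difference from placebo and no combined REGN5069 group. Sections 5.8.1 to 5.8.3 do name a combined group. The SAP's 95% confidence rule stands in 5.7, under efficacy methods.

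SAP V2.0 was written after the week-12 results were known, and it calls that look the interim analysis. Section 2.3 records: "As the Interim Analysis showed no treatment effect, and there were no safety signals observed, it was decided to terminate the study" once the last patient reaches week 36. Section 1.2.4.2 says that "there were no new safety findings or concerns associated with REGN5069". Table 2 gives the two reasons together, no treatment effect and no safety signal, for ending the 52-week extension. For some deletions it gives only the safety reason, for example: "As at the IA there were no safety issues detected, there is no further need to summarize non-serious AEs separately". The laboratory shift tables and several criteria for potentially clinically significant values go on the same ground.

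**The concern.** An endpoint defined as a comparison ends up with no comparative estimate and no statement of how large an incidence, or how large an increase over placebo, the data rule out. Under 5.8.8 as written, 0/80 prints as 0% and 1/80 as 1.3%. Read without limits, either figure looks more reassuring than it is.

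This matters more because the absence of a signal is already put to use in V2.0. It is one of two reasons for ending before the week-52 call, which the protocol's Amendment 1 had added on health authority feedback to learn about joint replacement. It is the only reason of substance for removing several safety outputs. No bound accompanies any of these steps. If the report repeats that no signal was seen, the reader needs the upper limit to know what the statement is worth.

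**Working it through.** **Inputs.** SAP 2.2: "Up to approximately 240 patients (80 per treatment group) are randomized to 3 treatment groups in a 1:1:1 allocation", so 160 patients for the two doses combined. The same section assumes 15% dropout: 80 × 0.85 = 68 and 160 × 0.85 = 136. The two-sided 95% level is the one that SAP 5.7 uses for efficacy. The event counts below are illustrations, because the documents report no arthropathy counts or rates.

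**1. The plan's own figure.** SAP 2.2 begins "Assuming a standard deviation (SD) of 2.3" and states that "80 patients per treatment group provides approximately 80% power to detect a treatment difference of 1.1" on WOMAC pain. With 68 evaluable patients per arm:

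- Standard error = 2.3 × √(2/68) = 0.394
- 1.1 / 0.394 = 2.789
- Power ≈ Φ(2.789 − 1.960) = Φ(0.829) = 79.6% (79.1% with the t distribution)

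The stated figure reproduces. It concerns efficacy only. No rate, margin or precision is stated anywhere for arthropathy.

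**2. Upper limit with zero cases.** With no events, the Clopper-Pearson two-sided 95% upper limit is 1 − 0.025^(1/n).

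| Result | Calculation | Upper limit |
|---|---|---|
| 0/80, one arm | 1 − 0.025^(1/80) | 4.51% |
| 0/160, combined REGN5069 | 1 − 0.025^(1/160) | 2.28% |
| 0/68, one arm after dropout | 1 − 0.025^(1/68) | 5.28% |
| 0/136, combined after dropout | 1 − 0.025^(1/136) | 2.68% |

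For 1/80 (1.25%) the exact interval is 0.03% to 6.77%.

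**3. Difference from placebo.** The Newcombe interval for a difference d = p1 − p2, with Wilson limits (l, u) for each arm, is

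- lower = d − √[(p1 − l1)² + (u2 − p2)²]
- upper = d + √[(u1 − p1)² + (p2 − l2)²]

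For 2/80 against 1/80:

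- p1 = 0.0250, Wilson limits 0.0069 to 0.0866
- p2 = 0.0125, Wilson limits 0.0022 to 0.0675
- d = 0.0125
- lower = 0.0125 − √(0.0181² + 0.0550²) = −0.045
- upper = 0.0125 + √(0.0616² + 0.0103²) = +0.075

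The interval is about −4.5 to +7.5 percentage points. With no cases at all, the upper limit for the difference is +4.6 points for 0/80 against 0/80, and +2.3 points for 0/160 against 0/80.

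**4. What had been imaged by week 12.** Protocol Table 1 schedules radiographs of both knees, both hips and both shoulders at screening and at week 36. At week 12 it schedules a radiograph and an MRI of the index knee only. Of six joints radiographed at screening, one was due for repeat imaging by the week-12 visit.

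**5. Whether Kaplan-Meier fills the gap.** It is conditional on the data, and 5.8.8 specifies no confidence limits for it. With zero events the curve does not move and gives no useful upper bound.

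**The case against.** The strongest reply is that the plan never claims more than it shows, and much of this stands.

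- **A reader might infer that the sponsor stopped on a safety conclusion, or treated arthropathy risk as excluded.** The documents do not support that. SAP 1.2.4.2 rests the decision to discontinue on failure to show benefit. The safety wording reports what was seen. An independent committee that includes imaging expertise reviews unblinded data.
- **A reader might infer that arthropathy follow-up was cut.** It was not. All patients continue to week 36, when the full radiograph set and the index-knee MRI are due. The week-52 call had no scheduled imaging. Table 2 lists no change to 5.8.8, and it adds several adverse-event summaries.
- **Calling the plan bare counts would be unfair.** It has breakdowns by type, listings and the conditional Kaplan-Meier analysis. SAP 4.6 lists time to accelerated and to destructive arthropathy.
- **Calling arthropathy the trial's main safety risk goes too far.** Protocol 3.2.1 finds no present evidence linking it to GFRα3 blockade and describes the monitoring as precautionary. No adverse event of special interest is defined.
- **A reader might infer that the sample would miss most relevant increases.** The documents state neither a background rate nor a relevant increase, so this cannot be established. The answer depends on the assumption chosen. Two-sided Fisher power is 11% for an assumed 1% against 5% with 80 per arm, and 82% for an assumed 1% against 10% with the doses combined. The SAP plans no such test.
- **The week-12 coverage point has limits.** Imaging for worsening pain was available, early-termination visits provide for imaging all the joints, and the joint pain questionnaire covers knees, hips and shoulders from week 2. Patients enrolled early may already have been past week 12.

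Finally, counts with denominators let any reader derive an exact interval, and Protocol 10.4.4.2 itself plans only numbers and percentages. That is true, and it limits the seriousness of the point. It does not answer it: the endpoint is comparative, and the plan leaves the comparison to the reader.

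**Conclusion.** The point holds as a gap in the analysis specification. SAP 5.8.8 yields no interval, no contrast with placebo and no combined REGN5069 estimate for adjudicated arthropathy. V2.0 meanwhile relies on the absence of a signal, jointly with lack of efficacy for ending before week 52 and by itself for removing several safety outputs.

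The size is a matter of precision. Zero cases would leave incidences up to about 4.5% open for one dose and 2.3% for both doses together, or 5.3% for one dose at 68 patients. These figures assume that the planned 80 per arm were treated and assessed, or 68 if the 15% dropout assumption is applied to imaging. The limits need no assumed event rate. No statement about power for arthropathy follows from the documents, and the efficacy conclusion is not affected.

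**What to change.** In SAP 5.8.8:

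1. Report patients with adjudicated arthropathy (any accelerated arthropathy, destructive arthropathy, and each type) for each arm and for combined REGN5069, with exact (Clopper-Pearson) 95% intervals.
2. Add the 95% interval (Newcombe or Miettinen-Nurminen) for the risk difference from placebo, for each dose and for the combined group.
3. Where the arthropathy result is described as showing no signal, give the upper limit in the same statement.

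The change log in 1.2.4.2 records the reasons for a past decision and need not be rewritten. The cost is a few more columns in one existing table, with no new data, patients or procedures. The one drawback for the sponsor is a safety statement that looks less favourable.

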**Figure 1: Study Flow Diagram**

a - Study drug is to be administered every 4 weeks throughout the 12-week treatment period. Thus, study drug is to be administered at the day 1 (baseline) visit and at the week 4 and week 8 visits.

The Schedule of Events table is presented in Appendix 11.1, [Table 3](#).

### **3. ANALYSIS POPULATIONS**

In accordance with guidance from the International Council for Harmonization of Technical Requirements for Registration of Pharmaceuticals for Human Use (ICH) guideline ICH E9 Statistical Principles for Clinical Trials (1998), the following populations are used for all statistical analyses:

#### **3.1. Full Analysis Set (FAS)**

The full analysis set (FAS) includes all randomized patients and is based on the treatment allocated (as randomized). Efficacy endpoints are analyzed using the FAS.

#### **3.2. The Safety Analysis Set (SAF)**

The safety analysis set (SAF) includes all randomized patients who received any study drug and is based on the treatment received (as treated). Treatment compliance/administration and all safety variables are analyzed using the SAF.

Determination of "as treated" is done as follows:

- Patients randomized to the placebo arm who receive at least one dose of active REGN5069 1000mg will be considered as treated with REGN5069 1000mg.
- Patients randomized to the placebo arm who receive at least one dose of active REGN5069 100mg and no dose of REGN5069 1000mg will be considered as treated with REGN5069 100mg.
- Patients randomized to any of the REGN5069 arms that did not receive any dose of either REGN5069 1000mg or 100mg will be considered as treated with placebo and classified in the placebo treatment arm for the purpose of analysis using the SAF.

#### **3.3. The Pharmacokinetic Analysis Set**

The PK analysis set includes all treated patients who received any study drug and who had at least 1 non-missing drug concentration measurement following the first dose of study drug. Patients are analyzed according to the treatment actually received (as treated).

#### **3.4. The Immunogenicity Analysis Set**

The anti-drug antibody (ADA) analysis set (AAS) includes all treated patients who received any study drug and had at least one non-missing ADA result from the REGN5069 ADA assay after the first dose of study drug. Patients will be analyzed according to the treatment actually received.

## 4. ANALYSIS VARIABLES

### 4.1. Demographic and Baseline Characteristics

The following demographic and baseline characteristic variables are to be summarized by treatment group:

- Age at screening (years)
- Age category (<65, >=65 years)
- Sex (Male, Female)
- Race (American Indian/Alaskan Native, Asian, Black/African American, Native Hawaiian/Other Pacific Islander, White, and Other)
- Ethnicity (Hispanic or Latino, Not Hispanic or Latino, Not Reported)
- Baseline Weight(kg)
- Baseline Height(cm)
- Baseline Body mass index (BMI) calculated from weight and height
- K-L screening score of index knee, as per the electronic data collection system (EDC) (and by the integrated response system (IRT) if different)
- Subjects participating in the MOTICON sub-study
- WOMAC pain subscale at baseline.
- Geographic region: USA, MGU (Republic of Moldova, Georgia, Ukraine), and Poland
- Duration of OA at baseline
- Walking aid use at baseline
- History of analgesic intolerance and inadequate pain relief

### 4.2. Medical History

Medical history was recorded at screening and is to be coded to a Preferred Term (PT) and associated primary System Organ Class (SOC) according to the Medical Dictionary for Regulatory Activities (MedDRA®) Version 23 or later.

### 4.3. Prior/Concomitant Medications and Procedures

Prior medication and procedures were collected at the screening visit as medication and procedure history. Any treatment administered and/or procedures performed from screening to the end of the follow-up period is considered concomitant medication and/or procedures, respectively. This includes medications and/or procedures that were started before the study and are ongoing during the study. These are to be analyzed as per the study observation periods defined in Section 5.

Medications are coded to the Anatomical Therapeutic Chemical (ATC) level 2 (therapeutic main group) and ATC level 4 (chemical/therapeutic subgroup), according to WHO Drug Dictionary (WHODD) Version REGGENERONWHOB3Global202003 or higher. Patients are counted once in all ATC categories linked to the medication.

#### Medication/Procedure Classifications

*Prior medications/procedures* are defined as medications administered and/or procedures performed starting prior to the patient signing the informed consent form (ICF).

*Pre-treatment concomitant medications/procedures* are defined as medications administered and/or procedures performed starting as follows:

*On-treatment concomitant medications/procedures* are defined as any treatment administered and/or procedures performed after the administration of first dose until 28 days after administration of last dose.

*Follow-Up concomitant medications/procedures* are defined as medications administered and/or procedures performed after the on-treatment period, and up to Week 36 Visit.

- for opioids, the pre-treatment period is defined as starting 4 weeks before ICF
- for genicular nerve block and any other similar procedures, it is defined starting 3 months before ICF
- for the rest of concomitant medications/procedures, starting on or after the patient signing the informed consent form (ICF)

and until before the first dose of study drug

#### **4.3.1.      Rescue Medication and Prohibited Medication and Procedures During the Study**

##### Rescue Medication

Starting at the screening visit until after the week-24 study visit is completed, acetaminophen is the only study-permitted rescue medication. Acetaminophen tablets of selected brand and strength are being provided to patients by the study site for use as rescue medication for breakthrough OA pain. In advance of initiating the study, each study site must consult with the sponsor and select the brand and the strength of acetaminophen tablets that are to be dispensed to patients as rescue medication. In the event that pain relief for OA pain is inadequate, patients are to take acetaminophen, as needed, in accordance with the instructions provided with the medication by each study site, with a maximum of 3000 mg/day. To prevent liver damage, the maximum allowed daily dose of 3000 mg of acetaminophen must not be exceeded and excessive alcohol consumption must be avoided. The use of rescue medication is not allowed for 48 hours prior to the start of or during a scheduled study visit to minimize the confounding effects of rescue medication on efficacy measures.

